2.7 Statistical Analysis and Sample Size Justification	
The data will be analyzed by the Investigator and Co-investigator.
 
Main outcomes will be ISI, CAPS nightmare frequency and total score, diary and PSG sleep latency and WASO at week 3 and for non-PSG variables Med week 6. We will also explore effects on REM and SWS and their relationships to other study outcomes.
 
An alpha level of .05 (one-tailed) will be applied in testing Hypotheses 2a), 2b), 2d), and 2e). Initially, data will be pre-screened for errors, outliers, normality of distributions, and any necessary modifications, such as transformation of variables and/or elimination of cases, will be conducted.
 
Our initial objectives are descriptive. We will generate frequencies of types of trauma exposures associated with insomnia and the rates for PTSD diagnoses and sub-diagnostic threshold PTSD symptoms in the recruited study population (Objective 1) and the frequency of adverse events (Objective 2). The latter will be descriptively contrasted to the extant data for suvorexant from the insomnia registry trials as a guide to planning future trials including dosing.
 
Hypothesis 2a) Insomnia will improve, and nightmares and other PTSD symptoms will be reduced with suvorexant treatment compared with placebo: We will compare baseline characteristics of the treatment groups using independent samples t-tests for continuous variables or chi-square tests for categorical variables. If a significant group difference is found in some of the variables, the variable(s) will be included in subsequent analyses as a covariate(s). We will perform 2 (Group) x 3 (Time: baseline, Med week 3, and week 6) mixed ANOVAs or ANCOVAs [if there is a covariate(s)] to compare the changes in ISI scores, nightmare frequency, and CAPS scores, separately, between the two groups.
 
Hypothesis 2b) Improved sleep will be associated with reduced non-sleep PTSD symptoms: Correlation coefficients between baseline – Med week 6 changes in sleep measures (e.g., ISI scores and nightmare frequency) and changes in the CAPS scores excluding two sleep-related items will be computed. In addition, we will exploratively examine if there is an interaction with treatment condition by performing regression analyses in which CAPS scores will be predicted by changes in sleep measures, treatment condition, and a Sleep measure X Treatment condition interaction.
 
Hypothesis 2d) Sleep latency and wake after sleep onset (WASO) will be reduced with suvorexant treatment compared with placebo: We will perform 2 (Group: suvorexant vs. placebo) x 2 (Time: Baseline and Med week 3) mixed ANOVAs or ANCOVAs [if there is a covariate(s)] to compare the changes in PSG measured sleep latency and WASO between the suvorexant and placebo groups.
 
Exploratory hypothesis 2e) When reduced at baseline (i.e., SWS below 100 minutes and mean REM segment duration below 15

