
	
minutes), SWS and the duration of continuous segments of REM sleep will increase with suvorexant than placebo: Participants with reduced baseline SWS (below vs. above 100 minutes) and mean REM segment duration (below vs. above 15 minutes) will be included in the analyses. 2 (Group) x 2 (Time: Baseline and Med week 3) mixed ANOVAs or ANCOVAs will be performed to compare treatment changes in SWS and REM segment duration between the suvorexant and placebo groups.
 
Power Considerations:
 
G*Power 3.1 ³³ was used to conduct power analysis.
 
Power analysis for Hypothesis 2a) is based on the effect size estimated using findings of Herring and colleagues' ²² placebo controlled trial of suvorexant in adults with insomnia. Since there are no data for suvorexant on trauma related nightmares and PTSD symptoms, we also used Taylor and colleagues' ²⁴ placebo controlled trial of prazosin in civilian outpatients with PTSD, sleep disturbances, and nightmares. Taylor et al. found a large-size effect of prazosin on changes in trauma-related nightmare severity compared with placebo ($d = 0.96$ or $f = 0.48$) and PTSD severity ($d = 0.79$ or $f = 0.40$) and a medium-size effect on changes in trauma-related insomnia symptoms severity ($d = 0.50$ or $f = .25$). Herring and colleagues found a small-size effect of a 1-month suvorexant treatment (20mg for nonelderly and 15mg for elderly) on insomnia severity measured by the ISI ($d = 0.39$ or $f = 0.20$). To detect an $f = 0.20$ Group x Time interaction effect in the proposed mixed ANOVA with 80% power, a total of 42 participants are needed.
 
Power analysis for Hypothesis 2b) is based on the effect sizes estimated using Krakow and colleagues' findings ³⁴ from their study examining effects of cognitive behavioral therapy for nightmares and insomnia in crime victims with PTSD. They found correlations between changes in nightmare frequency, insomnia severity, and sleep quality and changes in overall PTSD symptom severity ranging from $r = .37$ to $.40$. A sample size of 43 will allow for detecting similar size effects with 80% power.
 
Power analysis for Hypothesis 2d) is based on findings from the aforementioned Herring and colleagues' study. They found that effects of suvorexant on sleep latency and WASO were $f = 0.17$ and 0.31, respectively. To detect an effect size of 0.17 using the proposed mixed ANOVA with 80% power, a total of 70 participants are needed.
 
Power analysis for Exploratory hypothesis 2e) is based on findings from the aforementioned Taylor and colleagues' study. They found that the effect of prazosin on mean REM period duration was $f = 0.50$. Using the proposed mixed ANOVA, a total of 16 participants will allow for detecting a large size within-between interaction effect ($f = 0.50$) with 80% power.

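### Hypothesis 2b is tested by a change-score correlation that ignores treatment arm, so a significant result may partly restate Hypothesis 2a

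*Combined protocol and SAP*

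**What the plan says.** Section 2.7 (Statistical Analysis and Sample Size Justification) makes 2b an inferential test: "An alpha level of .05 (one-tailed) will be applied in testing Hypotheses 2a), 2b), 2d), and 2e". The test consists of "Correlation coefficients between baseline – Med week 6 changes in sleep measures", such as ISI and nightmare frequency, against CAPS change: "changes in the CAPS scores excluding two sleep-related items will be computed". Arm is not mentioned.

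Treatment enters only in an added step: "we will exploratively examine if there is an interaction with treatment condition". In that regression, "CAPS scores will be predicted by changes in sleep measures, treatment condition, and a Sleep measure X Treatment condition interaction". The outcome is given without the word change, a visit, a baseline covariate or the exclusion of the sleep items.

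Under Power Considerations, the 2b sample size comes from reported correlations of .37 to .40: "A sample size of 43 will allow for detecting similar size effects with 80% power". Section 2.5 (Assessments) lists the CAPS outcomes as the nightmare item and the total without the sleep items. In section 2.1, Hypothesis 2a expects suvorexant to improve insomnia and to reduce nightmares and other PTSD symptoms relative to placebo.

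**The concern.** A correlation taken over both arms mixes two things: whether patients whose sleep improves more also have a larger fall in non-sleep symptoms, and whether the two arms differ in mean change on both measures. The second is already the subject of Hypothesis 2a. If suvorexant works on both measures, the arm difference alone produces a correlation, and in the direction that the one-tailed test looks for. A significant 2b result would then be read as a patient-level link between better sleep and fewer daytime symptoms, when it may partly be 2a reported a second time.

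The added regression does not settle this as written. It is exploratory and targets the interaction. With the interaction in the model and no centring stated, the sleep coefficient under 0/1 coding of arm is the slope in one arm only, not an arm-adjusted overall association.

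**Working it through.** **1. The plan's own figure.** For a single correlation with r = .37, one-tailed alpha .05 and 80% power, Fisher's z gives N = ((1.645 + 0.842)/atanh(.37))² + 3 = 43.98, so 44. Simulating the one-tailed t test of a bivariate-normal correlation gives power 0.800 at N = 43. The stated 43 therefore reproduces. A two-sided calculation gives 56 and does not reproduce it. The power statement thus treats the sample as one group, which supports reading the correlation as pooled over arms.

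**2. Inputs.**
- From Power Considerations: d = 0.39 (suvorexant, ISI); from the prazosin study, d = 0.50 (insomnia symptoms), 0.96 (nightmares) and 0.79 (PTSD severity).
- From section 2.5: 70 participants expected to be retained.
- Assumed: 1:1 allocation (the ratio is not stated); each d is a standardized difference in change with equal SDs; within-arm correlation is zero. One scenario also assumes d = 0.39 for CAPS.

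**3. Correlation induced by arm alone.** With equal arms and no within-arm correlation,

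r = (d1·d2/4) / √[(1 + d1²/4)(1 + d2²/4)].

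- 0.39 and 0.39: 0.0380/1.0380 = 0.037
- 0.39 and 0.79: 0.0770/√(1.0380 × 1.1560) = 0.070
- 0.50 and 0.79: 0.0988/√(1.0625 × 1.1560) = 0.089
- 0.96 and 0.79: 0.1896/√(1.2304 × 1.1560) = 0.159

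**4. One-tailed rejection rate when there is no association within arms** (nominal 5%; 100,000 simulated trials per row).

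| d sleep / d CAPS | Pooled r | Pooled, N = 43 | Pooled, N = 70 | Arm-adjusted, both N |
|---|---|---|---|---|
| 0 / 0 | 0 | 5.0% | 4.9% | 4.9–5.0% |
| 0.39 / 0.39 | 0.037 | 8.0% | 9.0% | 4.9–5.0% |
| 0.39 / 0.79 | 0.070 | 11.7% | 14.3% | 5.0% |
| 0.50 / 0.79 | 0.089 | 14.2% | 18.2% | 4.9–5.0% |
| 0.96 / 0.79 | 0.159 | 27.1% | 37.9% | 4.9–5.0% |

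If either d is zero, the formula in step 3 gives r = 0 and the pooled test keeps its 5%.

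A hand check for N = 70 uses Φ(atanh(r)·√67 − 1.645). For r = 0.070 it gives Φ(−1.07) = 0.14, and for r = 0.159 it gives Φ(−0.33) = 0.37, in line with the simulation.

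**5. Cost of adjusting for arm.** One covariate adds 1 to the Fisher z sample size: 43.98 + 1 = 44.98, so 45 in place of 44, against 70 expected to be retained.

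**The case against.** **2b claims only an association.** This is the strongest reply. The hypothesis makes no within-arm, causal or mediation claim, and a pooled correlation validly estimates the overall association. A reader might infer that the plan's test has a type I error of 14 to 38%. The documents do not support that: those rates are errors only against a null of no association within arms, which the plan does not state. What stands is the interpretation. The hypothesis speaks of improved sleep going with fewer symptoms, and a shift between arms does not show that for patients.

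**The larger rates rest on another drug.** The values 0.96 and 0.79 come from a prazosin study in PTSD. The plan says there are no suvorexant data on these outcomes and expects only about half of its sample to have PTSD. The 0.79 is for PTSD severity, not shown to be CAPS without the sleep items. This is fair, and the range properly starts at 5%.

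**The induced correlation is small.** At most 0.159, it explains 2.5% of variance (0.159² = 0.025), lies below the value of about 0.20 needed for one-tailed significance at N = 70, and is far below .37. Arm alone would not be expected to produce the planned correlation. It does make a chance crossing of the threshold more likely.

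**Shared items.** Because the regression says only that "CAPS scores will be predicted by changes in sleep measures, treatment condition" and the interaction, a reader might infer that its outcome is the raw total including the nightmare item, and that overlap with the sleep measure could produce a significant 2b result. The documents do not support this. The 2b correlation already excludes the two sleep items, section 2.5 defines the CAPS outcome without them, and the regression's wording is probably shorthand for the variable named one sentence before. What remains is an ambiguity to clear up.

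**Arm is already in a planned model.** It is, but that model is exploratory, aimed at the interaction and unclear in its outcome.

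**Conclusion.** The point holds as a matter of test choice and interpretation. The 2b correlation takes no account of arm, and under the effects that Hypothesis 2a expects, a significant result could partly restate 2a. At N = 70 with no within-arm association, the rejection rate is about 9% for d = 0.39 on both measures, 14% for 0.39 with 0.79, and 38% only if both prazosin-study values apply. If treatment leaves one measure unchanged it is 5%, and with arm adjustment it is 5% in every scenario.

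These figures assume 1:1 allocation, equal SDs and the planning effect sizes read as differences in change. That the correlation is pooled is inferred from the absence of any mention of arm and from the single-sample power figure. The treatment comparisons under 2a and 2d are not affected. The change is worth making because it needs no new data and almost no sample size.

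**What to change.** In section 2.7, define the 2b test as the sleep-change coefficient from a regression of baseline-to-week-6 change in CAPS minus the two sleep items on change in the sleep measure and treatment arm. Baseline CAPS minus sleep items may be added as a covariate but is optional. Add the sleep-by-treatment interaction only as a second, exploratory step. Name the same CAPS change score as the outcome in both steps, so that the text agrees with section 2.5 and with the correlation sentence. Report the pooled and within-arm correlations descriptively. Even then, the result is an association and not evidence of mediation.

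Cost: a wording change and about one degree of freedom (one more if baseline is included). The required N rises by about 1, against 70 expected to be retained.

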
2.1 Objectives & Hypotheses
	
Disturbed sleep is one of the most common and distressing responses to exposure to severe trauma and can persist in many of those affected with and without accompanying posttraumatic stress disorder (PTSD). Insomnia is a risk factor for many of the conditions that are prevalent in trauma-exposed populations including PTSD, depression, and physical health conditions such as obesity, and cardiovascular disease. Trauma-related insomnia (TRI) is not typically differentiated in studies characterizing insomnia and its treatment, and insomnia accompanying PTSD has been shown to be relatively refractory to the treatments that are established for PTSD. Thus treatment of TRI presents an unmet need that has implications for the large and growing groups of people exposed to trauma in terms of relieving distress and preventing further psychiatric and medical morbidity.
 
Most of the data on TRI comes from research on populations with PTSD. Difficulty initiating and maintaining sleep is designated as one of the heightened arousal symptoms of PTSD in the DSM. Sleep studies have suggested reduced slow wave sleep (SWS) in some PTSD populations and fragmented rapid eye movement (REM) sleep when PTSD is developing, and during its more acute stages. Suvorexant is a first in class orexin antagonist and is approved by the FDA for the indication of insomnia. Orexin antagonists dampen the activity of a specific arousal enhancing system in the brain during sleep. In rodent models suvorexant has been shown to enhance, and in healthy humans, to not affect slow wave and REM activity (in contrast with traditional hypnotics which can diminish both). Reducing arousal during sleep while maintaining REM and slow wave sleep is a promising profile for the treatment of TRI. We are therefore proposing a placebo controlled evaluation to assess the efficacy of suvorexant for treating TRI with and without PTSD and its tolerability in these populations. We will include polysomnography (PSG) in order to probe potential mechanisms and biomarkers predicting response. The proposed study will meet the objectives below and test the following hypotheses:
 
Objective 1. To recruit a group of participants that meet criteria for insomnia and who identify a severely threatening event (DSM criterion A trauma) as a precipitant or a factor that significantly exacerbated their sleep disturbance; and to determine the frequency of PTSD diagnoses and symptoms among the recruited participants.
 
Hypothesis 1) – Recruitment will reveal TRI to be a common condition that in approximately half of cases occurs absent PTSD.
 
Objective 2. To evaluate the effectiveness and tolerability of suvorexant on insomnia and when present, associated PTSD symptoms and its effects on PSG measures in participants with TRI.
 
Hypothesis 2a) Insomnia will improve, and nightmares and other PTSD symptoms will be reduced with suvorexant treatment compared with placebo.
 
2b) Improved sleep will be associated with reduced non-sleep related PTSD symptoms when present.

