
	
2c) Suvorexant will be well tolerated by the participants.
 
2d) Sleep latency and wake after sleep onset (WASO) will be reduced with suvorexant treatment compared with placebo.
 
2e) (exploratory hypothesis) When reduced at baseline (i.e. SWS below 100 minutes and mean REM segment duration below 15 minutes) SWS and the duration of continuous segments of REM sleep will increase with suvorexant compared with placebo.

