these data we predict that suvorexant will not precipitate REM sleep-related parasomnias in the proposed target population but rather will consolidate fragmented REM sleep periods that have been observed in the earlier stages of PTSD. This would be similar to the effects seen for the alpha 1 adrenergic antagonist prazosin, an agent that targets central noradrenergic arousal promoting mechanisms and has been shown to reduce the severity of nightmares and related sleep disruption with PTSD. Specifically, the only study that monitored EEG sleep found lengthened discreet REM sleep periods with increases in the amount of REM sleep that were proportionate to the increases in overall sleep time. Prazosin, however, did not reduce time to fall asleep in this study.²⁴ Given the data from animals and that the absence of changes was in healthy volunteers, we hypothesize that suvorexant will also enhance SWS when it is deficient at baseline.

Summary of Significance

Insomnia is quite common among those exposed to trauma. PTSD usually features insomnia symptoms and insomnia precipitated or exacerbated by trauma is also common absent a PTSD diagnosis. TRI does not appear to respond well to previously available treatments. Fragmented patterns of REM sleep have been observed during the development of PTSD and within several years of its onset. Suvorexant is promising for maintaining overall sleep and REM sleep that is being disrupted by heightened arousal. In addition to proposing a placebo-controlled evaluation of efficacy and tolerability of suvorexant for TRI we further propose utilizing PSG to potentially elucidate physiological biomarkers of treatment response. Given the rising toll of trauma this proposal is a timely response to Merck's call for proposals for "clinical studies exploring the investigational use of suvorexant in key insomnia subpopulations."

2.3 Study Design	A double-blind placebo-controlled 6-week trial of suvorexant 10 – 20mg for trauma related insomnia (with and without PTSD) with polysomnography								
-------------------------	---	--	--	--	--	--	--	--	--

2.4 Study Flowchart	(Visits)	Prescreen	Screen	Baseline	Med Week 1	Med Week 2	Med Week 3	Med Week 6	Post-Rx Week1
	Phone screen	X							
	Physical		X						
	Wt. & Vital Signs		X		X	X	X	X	X
	DSISSD and SCID		X						
	LEC		X						
	CAPS			X			X	X	
	ISI			X			X	X	X
	Sleep Diaries			X (1 week)	X		X	X	X(1week)
	PSG			XX			X		
	AE				X	X	X	X	X

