--	--

Adverse Event Screening At each medication visit participants will be queried regarding the presence of any new symptoms or concerns. We will specifically query the adverse effects that occurred at a frequency that exceeded placebo in either the 3 month pivotal trials²² or the 1-year study²³ including somnolence, fatigue, dry mouth, dyspepsia, and peripheral edema. We will also specifically query the pre-specified events of interest for those trials including suicidal ideation, complex sleep-related behaviors (e.g. getting food during the night and not remembering it), sleep onset or off-set hallucinations, sleep paralysis, and falls. Excessive daytime sleepiness will be assessed by administering the Epworth Sleepiness Questionnaire.³¹ Weight and vital signs will be obtained at each study visit. At the post-treatment visit specific inquiry will also include the occurrence of common medication withdrawal symptoms such as dizziness, shaking, nausea, and muscle tension as well as re-assessment of insomnia and sleep patterns for that period.

Polysomnography (PSG):

PSG collection includes a standard electroencephalogram (EEG) montage with two central, frontal, and occipital leads, two electrooculograms, chin and limb electromyograms, and an electrocardiogram (ECG). Recordings will be conducted using an Embla (Denver, CO) Titanium unit in the CRU. Screening for sleep disordered breathing and limb movements will be performed using the screening night data. Visual scoring of sleep records from a computer monitor will be done following the American Academy of Sleep Medicine (AASM) Manual, Version 2.0.³² The REMLogic software (Embla) will calculate sleep parameters including TST, SOL, WASO, the percentage of each sleep stage, and mean duration of continuous REM segment. Calculation of REM segment length used our previous criteria¹⁶ of at least two epochs of consecutive REM sleep with no more than one 30-sec epoch of non-REM sleep interruption. The sleep parameters for baseline will be obtained from the second night recording after an accommodation recording that will also screen for apnea will be used in data analysis. Respiratory strain gauge, nasal air flow, and oximetry monitors will be included on the first but not subsequent nights. Participants will be instructed to go to bed near their habitual bedtimes and will wake up naturally. PSG will be done prior to medication and after 3 weeks of medication treatment to allow for stable dosing.

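### Exploratory hypothesis 2e, read literally, analyses only participants low on both sleep measures, and no specified model crosses baseline PSG with treatment, so dependence on deficiency and the biomarker aim have no planned test

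*Combined protocol and SAP*

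**What the plan says.** Hypothesis 2e in section 2.1 is labelled exploratory and is conditional on a low baseline: "When reduced at baseline (i.e. SWS below 100 minutes and mean REM segment duration below 15 minutes) SWS and the duration". The prediction is that both measures, SWS and the length of unbroken REM segments, rise compared with placebo. Section 2.2 (Rationale for suvorexant) gives the reasoning: animal data show an increase, the human data without change came from healthy volunteers, and so "we hypothesize that suvorexant will also enhance SWS when it is deficient at baseline".

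Section 2.7 defines who is analysed: "Participants with reduced baseline SWS (below vs. above 100 minutes) and mean REM segment duration (below vs. above 15 minutes) will be included". The model follows: "2 (Group) x 2 (Time: Baseline and Med week 3) mixed ANOVAs or ANCOVAs will be performed to compare treatment changes in SWS". The REM endpoint is compared between arms in the same way. The two brackets contrast below with above, but the model has no below/above factor. The baseline value is a single recording, taken after an accommodation night: "The sleep parameters for baseline will be obtained from the second night recording" (section 2.5, Polysomnography).

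Section 2.1 also states a purpose for the recordings: "We will include polysomnography (PSG) in order to probe potential mechanisms and biomarkers predicting response". The Summary of Significance in section 2.2 repeats it in softer terms. In section 2.7 the nearest counterpart is one sentence saying that effects on REM and SWS, and how these relate to the other outcomes, will be explored. It names no model, no baseline predictor and no definition of response.

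**The concern.** There are three separate problems.

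**Who is in the 2e analyses.** Joined by the word *and*, the two conditions apply together. A participant with SWS of 80 minutes and REM segments of 16 minutes would then be left out of the SWS analysis because of a measure that has no bearing on it. Two analysts could build different data sets from this sentence.

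**What a positive 2e result could mean.** The rationale contrasts healthy sleepers, in whom no change was seen, with deficient sleepers, in whom a gain is expected. A test confined to deficient sleepers gives the same positive result whether the effect is specific to them or uniform. It cannot tell the two apart.

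**The biomarker aim.** Predicting response to suvorexant, as opposed to predicting who improves in either arm, requires a baseline-by-treatment term with a clinical outcome. None is specified. Any later statement that baseline REM or SWS identifies who benefits would be post hoc.

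**Working it through.** **1. The plan's own figure for 2e.** Section 2.7 states that 16 participants give 80% power at f = 0.50, an effect taken from a prazosin trial's REM period duration. For a Group x Time interaction with two groups, m time points and correlation ρ, the noncentrality is λ = f² · N · m / (1 − ρ), with df1 = m − 1 and df2 = (N − 2)(m − 1). The plan does not state ρ. With ρ = 0.5 and F-test alpha 0.05:

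- f = 0.20, m = 3 gives N = 42, as stated for 2a.
- f = 0.17, m = 2 gives N = 70, as stated for 2d.
- f = 0.50, m = 2 gives N = 12, not 16. At N = 16, λ = 0.25 · 16 · 2 / 0.5 = 16 and power is 0.96.

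N = 16 does appear at 80% power with ρ = 0.2. The stated figure is therefore on the cautious side for that effect size. It matters here only as the plan's own minimum for 2e.

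**2. Size of the analysis set.** Inputs: 70 retained (section 2.5). The share p below each cut-off is not given, so a range is assumed, with the same p for both measures and a correlation between them of 0 to 0.5 (bivariate normal). At correlation 0 the joint set is 70 · p².

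| p below each cut-off | One measure, 70 · p | Both measures, correlation 0 | Both measures, correlation 0.5 |
|---|---|---|---|
| 30% | 21 | 70 · 0.09 = 6.3 | 11 |
| 50% | 35 | 70 · 0.25 = 17.5 | 23 |
| 70% | 49 | 70 · 0.49 = 34.3 | 39 |
| 80% | 56 | 70 · 0.64 = 44.8 | not needed |

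At 50% and independence, the joint rule halves the set for each endpoint. At 30% it falls below the plan's own 16. At 80% the loss is modest (45 against 56).

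**3. Is baseline PSG crossed with treatment anywhere in section 2.7?**

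- 2a: Group x Time on ISI, nightmares and CAPS. No baseline PSG term.
- 2b: a regression with a treatment interaction, but the predictor is the change in sleep measures (ISI and nightmares are the examples) and the outcome is CAPS.
- 2d: Group x Time on PSG sleep latency and WASO.
- 2e: Group x Time within the low-baseline set.
- Covariates enter only where the arms differ significantly at baseline, and then as main effects.

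None of these contains the term. Since 2b does write out an exploratory interaction, the same detail for the biomarker aim would be in keeping with the rest of the plan.

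**4. What an interaction test could deliver.** Assumptions: all 70 kept, 1:1 allocation (the ratio is not stated), one-sided 0.05, ρ = 0.5, and baseline split at the cut-off for simplicity. The effect on the change score in SD units is d = 2f · √(2 / (1 − ρ)) = 4f. With n1 below and n0 above the cut-off, the standard error of the difference in effects is √(4/n1 + 4/n0), on 66 df. For n1 = n0 = 35 this is √(8/35) = 0.478. The ranges cover 23% to 70% of participants below the cut-off.

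| Effect below cut-off | Power if no effect above | Power if half the effect above |
|---|---|---|
| f = 0.50 (d = 2.0) | 0.97–0.99 | 0.54–0.67 |
| f = 0.25 (d = 1.0) | 0.54–0.67 | 0.22–0.27 |
| f = 0.17 (d = 0.68) | 0.32–0.41 | 0.15–0.17 |

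The interaction can be estimated, but it is well powered only if the very large borrowed effect is true and is absent above the cut-off.

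**The case against.** **2e is a conditional hypothesis.** It asks whether SWS and REM segments rise against placebo in those who start low. A randomised comparison within that subset answers this, because the subset is defined before treatment. A reader might infer that 2e cannot be answered at all; the documents do not support that. If the effect is uniform, reporting an effect in deficient sleepers is still true. Only a claim of specificity would be unsupported, and the plan makes none in so many words. This stands.

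**Selection on one night.** A reader might infer that choosing participants on a single recording invalidates the test. It does not. Selected participants drift upward at the next recording (about 0.15–0.58 SD for night-to-night correlations of 0.5–0.7), but equally in both arms; the simulated one-sided type I error in the selected subset was 0.046 against a nominal 0.05. The remedy below uses the same single-night baseline, so it would not remove measurement error either. This is not part of the point.

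**The joint rule is one reading.** The plan speaks of analyses and ANOVAs in the plural and names two outcomes, so each measure may have been meant to select its own set. The loss in step 2 depends on the literal reading and on assumed shares; at 50% the set of about 18 still exceeds 16. This stands as a reason to clarify the sentence.

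**PSG has other uses.** The recordings also supply the 2d outcomes and the screen for apnoea and limb movements, and the same sentence in section 2.1 mentions mechanisms as well as biomarkers. It would be wrong to infer that the nights are wasted. Biomarkers are not a numbered objective, and section 2.7 does promise some exploration. But that sentence specifies nothing that could be called a test of prediction, so the gap in the specified analysis remains.

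**Conclusion.** The point holds in limited form. The inclusion sentence for 2e is ambiguous and, read literally, drops participants who are relevant to each endpoint: about 18 kept instead of 35 if half of 70 fall below each cut-off independently, with a range that depends wholly on shares the documents do not give. The planned test is valid for the conditional question but cannot show that the effect depends on deficiency. The aim of identifying predictors of response has no specified analysis. This is a gap in the plan, not in the data, since the protocol schedules baseline PSG for every participant. As 2e is already exploratory, the matter is a worthwhile, low-cost improvement and does not threaten the main outcomes.

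**What to change.** 1. **Analysis sets.** If subsets are kept for 2e, select each endpoint on its own measure only: SWS below 100 minutes for SWS, mean REM segment below 15 minutes for REM segment duration.
2. **Dependence on deficiency.** In all participants with PSG data, regress week 3 SWS on arm, continuous baseline SWS and their product, and do the same separately for REM segment duration. Report the estimated treatment effect at low and high baseline values, using the 100-minute and 15-minute points for display only.
3. **Biomarker aim.** Regress ISI change from baseline to week 6 on arm, baseline ISI, baseline SWS (or, in a separate model, REM segment duration) and the product of that PSG measure with arm.
4. **Reporting.** Label all of these exploratory, give estimates with confidence intervals, and state that interaction power at 70 participants is low unless effects are very large.

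The cost is a few lines in section 2.7, with no new data or visits. The downside is four interaction estimates that will probably be imprecise and must not be presented as confirmatory.
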